### **8.5.3 Secondary Efficacy Analyses**

#### **8.5.3.1 Investigator's Assessment of Clinical Response at the TOC Visit in the mITT and CE-TOC Analysis Sets**

The number and percentage of subjects in each treatment group determined to have an IACR of success, failure, or indeterminate (and combined failure and indeterminate) at the TOC Visit will be presented for the mITT and CE-TOC Analysis Sets (indeterminates are excluded from the CE-TOC Analysis Set). Two-sided unadjusted 95% CIs for the difference in success rate will be calculated using a continuity corrected Z-test.

The reasons for IACR of failure at the TOC Visit will be summarized by treatment group for all subjects in the mITT and CE-TOC Analysis Sets. The reasons for IACR of indeterminate (subject lost to follow-up, missed visit, withdrew from the study or did not have CABP) will also be summarized by treatment group for all subjects at the TOC Visit for the mITT Analysis Set.

### **8.5.3.2 Early Clinical Response in the Microbiologic Intent-to-Treat Analysis Sets**

The number and percentage of subjects categorized as responder, non-responder and indeterminate (and combined non-responder and indeterminate) for the outcome of ECR will be presented for the microITT, microITT-2 and emicroITT Analysis Sets and a 2-sided unadjusted 95% CI for the difference in responder rate will be calculated using a continuity corrected Z-test.

The reasons for an ECR of non-responder and indeterminate at  $96 \pm 24$  hours after the first dose of study drug will be summarized by treatment group for all subjects in the microITT and microITT-2 Analysis Sets.

### **8.5.3.3 Investigator's Assessment of Clinical Response at the TOC Visit in the microITT and ME-TOC Analysis Sets**

The number and percentage of subjects in each treatment group determined to have an IACR of success, failure, or indeterminate (and combined failure and indeterminate) at the TOC Visit will be presented for the microITT and ME-TOC Analysis Sets (indeterminates are excluded from the ME-TOC Analysis Set). Two-sided unadjusted 95% CIs for the difference in success rate will be calculated using a continuity corrected Z-test.

The reasons for IACR of failure at the TOC Visit will be summarized by treatment group for all subjects in the microITT and ME-TOC Analysis Sets. The reasons for IACR of indeterminate at the TOC Visit will also be summarized by treatment group for all subjects in the microITT Analysis Set.

### **8.5.3.4 By-Pathogen Microbiological Response at the TOC Visit in the microITT and ME-TOC Analysis Sets**

The proportion of subjects with a microbiological response of success by baseline pathogen (and where relevant, the susceptibility phenotype) at the TOC Visit will be tabulated separately by treatment group for subjects in the microITT and ME-TOC Analysis Sets. Distinct pathogens are based on genus and species and where relevant, the susceptibility phenotype as defined in [Table 8](#).

For all by-pathogen analyses, subjects with a pathogen of the same genus and species with more than 1 phenotype, for example both MRSA and MSSA, will be counted once for each phenotype and once for the overall tabulation of the pathogen, for example, *Staphylococcus aureus*.

### **8.5.3.5 28-Day All-Cause Mortality in the ITT Analysis Set**

All-cause mortality through Study Day 28 will be summarized by treatment group in the ITT Analysis Set. Subjects who are lost to follow-up will be considered deceased for analysis and will be summarized separately on the table. A 2-sided unadjusted 95% CI will be calculated for the treatment difference in survival rates at Study Day 28 using a continuity corrected Z-test.

## 8.5.4 Additional Efficacy Analyses

Additional efficacy analyses will be conducted to support the efficacy findings for the primary and secondary efficacy outcomes. Confidence intervals for proportions will be determined for descriptive purposes, as indicated below, but no conclusions of NI will be made.

### 8.5.4.1 Clinical Outcome Measures

The proportion of subjects in each treatment group with an ECR of responder at  $96 \pm 24$  hours after the first dose of study drug will be determined by baseline pathogen (and where relevant, the susceptibility phenotype) in the microITT and microITT-2 Analysis Sets.

The number and percentage of subjects in each treatment group determined to have an IACR of success, failure, or indeterminate (and combined failure and indeterminate) at the TOC Visit in the microITT-2 and emicroITT Analysis Sets will be presented. A 2-sided unadjusted 95% CI for the difference in IACR success rate will be calculated using a continuity corrected Z-test.

The number and percentage of subjects in each treatment group determined to have an IACR of success, failure, or indeterminate (and combined failure and indeterminate) at the EOT Visit in the mITT, microITT, CE-EOT and ME-EOT Analysis Sets will be presented. A 2-sided unadjusted 95% CI for the difference in IACR success rates will be calculated using a continuity corrected Z-test.

The number and percentage of subjects in each treatment group determined to have an IACR of sustained success, relapse, prior failure or indeterminate (and combined relapse, prior failure and indeterminate) at the LFU Visit in the mITT, microITT, CE-LFU and ME-LFU Analysis Sets will be presented. Prior failure is defined as a subject who had an IACR of failure at the TOC Visit. A 2-sided unadjusted 95% CI for the difference in IACR sustained success rates will be calculated using a continuity corrected Z-test.

The proportion of subjects with an IACR of success will be presented by baseline pathogen (and where relevant, the susceptibility phenotype) at the TOC Visit in the microITT, microITT-2, and ME-TOC Analysis Sets. The proportion of subjects with an IACR of sustained success will be presented by baseline pathogen (and where relevant, the susceptibility phenotype) at the LFU Visit in the microITT and ME-LFU Analysis Sets. The proportion of subjects with an IACR of success will be presented by baseline pathogen (and where relevant, the susceptibility phenotype) at the EOT Visit in the microITT and ME-EOT Analysis Sets.

The proportion of subjects with an ECR of responder will be presented by baseline pathogens (and where relevant, the susceptibility phenotype) identified from blood specimens in the microITT Analysis Set. The proportion of subjects with an IACR of success will be presented by baseline pathogens (and where relevant, the susceptibility phenotype) identified from blood specimens at the TOC Visit in the microITT Analysis Set.

A summary (number and percentage of subjects) of the assessment of clinical signs and symptoms of CABP at each time point throughout the study will be presented by treatment group as a shift table compared to baseline in the ITT Analysis Set. If the EOT Visit and the last day of study drug are on the same day and only 1 assessment is performed, the assessment will be

summarized both at the study day and the EOT Visit. The proportion of subjects with resolution of all baseline signs and symptoms will also be provided by study visit (CAPB signs and symptoms were collected at baseline, daily while on study drug, at EOT, TOC and LFU). Analyses of signs and symptoms will only be assessed in subjects with non-missing assessments of all baseline signs and symptoms at the specified visit.

A summary of subjects who met the criteria for ECR responder will be provided by study visit. For each study visit, ECR will be determined for (ie, the denominator will consist of) those subjects who have died up through the relevant assessment, those subjects who have received an antibiotic for the treatment of CABP up through the relevant visit and those subjects with non-missing assessments of all baseline cardinal CABP symptoms at the relevant visit. If the EOT Visit and the last day of study drug are on the same day and only 1 assessment was performed, the assessment will be summarized both at the study day and the EOT Visit.

The number and percentage of subjects categorized as responder, non-responder and indeterminate (and combined non-responder and indeterminate) for the outcome of ECR plus improvement in vital signs, will be presented for the ITT Analysis Set and a 2-sided unadjusted 95% CI for the difference in responder rate will be calculated using a continuity corrected Z-test. The reasons for an ECR plus improvement in vital signs of non-responder and indeterminate at  $96 \pm 24$  hours after the first dose of study drug will be summarized by treatment group for all subjects in the ITT Analysis Set. Reasons for non-response include those for ECR (Section 8.5.1) as well as did not show an improvement in body temperature, hypotension, tachycardia and tachypnea. Reasons for indeterminate include no assessment of symptoms, did not have at least 2 cardinal symptoms of CABP at baseline and had no assessment of vital signs.

The proportion of subjects with an ECR of responder at  $96 \pm 24$  hours after the first dose of study drug by baseline pathogen (and where relevant, the susceptibility phenotype) and MIC to study drug received and by baseline pathogen (and where relevant, the susceptibility phenotype) and disk diffusion zone diameter will be determined for each pathogen isolated at baseline in the microITT Analysis Set.

The proportion of subjects with an IACR of success at the TOC Visit by baseline pathogen (and where relevant, the susceptibility phenotype) and MIC to study drug received and by baseline pathogen (and where relevant, the susceptibility phenotype) and disk diffusion zone diameter will be determined for each pathogen isolated at baseline in the microITT and ME-TOC Analysis Sets.

A concordance analysis of ECR and IACR at the TOC Visit by treatment group will be provided in the ITT Analysis Set.

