- b: Day 1 is the first day of study drug administration; subsequent study days are consecutive calendar days. Assessments/ procedures on Day 1 should be performed prior to first dose.
- c: INPATIENTS will be assessed daily while hospitalized; thus, data required for ECR Assessment (96 ± 24 hours after the first dose of study drug) will be collected.

  OUTPATIENTS must have a visit at the study site that is 96 ± 24 hours after the first dose of study drug to assess CABP signs and symptoms for calculation of ECR. Study personnel will inform subjects as to the timing of this visit during the course of daily telephone contact. In addition to the assessment of CABP signs/symptoms, subjects will also have the following procedures/assessments performed at that study site visit: ECGs, physical examination, AE monitoring, review of concomitant medications, vital signs, oxygen saturation, and blood sampling for PK analysis and safety laboratory evaluations. Importantly, study personnel will advise OUTPATIENTS not to take their first dose of study drug at home that day, rather to bring their blister packs (used and unused) to the study site where they will take their dose while supervised; thus, specific assessments can be performed both prior to and after taking the dose (i.e., ECGs and PK). See Footnotes i, k, l, m, o, p, and y below for details.
- d: Perform End of Treatment (EOT) assessments at the study site within 1 day (up to 2 days permitted) after the last dose of study drug or at the time of premature discontinuation of study drug or early withdrawal from study. EOT assessments resulting from premature discontinuation of study drug should be done in place of the regular study visit on Days 1 to 7.
- e: Perform Test of Cure (TOC) assessments at the study site 5–10 days after the last dose of study drug. All subjects will have a TOC Visit irrespective of early clinical failure or receipt of an alternative antibiotic.
- f: Perform Late Follow Up (LFU) assessments at the study site on Day 30 ± 3 days. All subjects will have a LFU Visit irrespective of early clinical failure or receipt of an alternative antibiotic.
- g: Obtain informed consent before initiating any study-specific assessments or procedures.
- h: Assessment or procedure may occur at either Screening OR prior to the first dose of study drug on Day 1 once eligibility has been determined.

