# 6.11 Assessment of Clinical Signs and Symptoms of CABP

Clinical signs and symptoms of CABP will be assessed at the time points specified in Table 1. Signs and symptoms are not obtained at TOC or LFU if the subject previously had an IACR of Failure.

The intensity of each symptom (dyspnea, cough, sputum production, and chest pain) will be evaluated and recorded as absent, mild, moderate or severe based on the definitions in Table 4 below. While Inpatient, all subjects will have clinical signs and symptom of CABP assessed daily.

Subjects who are discharged to home will be contacted by phone to assess signs and symptoms of CABP daily while on study drug with the following exception:

All subjects must have a study site visit  $96 \pm 24$  hours after the first dose of study drug to assess CABP signs and symptoms. Study personnel will inform Outpatients as to the timing of this required study site visit (see Section 6.1.1).

Table 4. Definitions of Symptom Intens
----------------------------------------

Symptom	Absent (0)	Mild (1)	Moderate (2)	Severe (3)
Dyspnea	Resolution (to pre-CABP baseline) or absence of dyspnea	Dyspnea on exertion (e.g., climbing stairs)	Dyspnea with normal/routine activities (e.g., walking)	Dyspnea at rest or requiring oxygen therapy
Cough	Resolution (to pre-CABP baseline) or absence of cough	Transient, does not interfere with normal activity	Frequent, interferes with normal activity or sleep	Constant, interferes with most or all activity or sleep
Production of purulent sputum	Resolution (to pre-CABP baseline) or absence of sputum production	Sputum production rarely causes difficulty or distress	Sputum production often causes difficulty or distress	Constant difficulty with sputum production
Chest pain	Resolution or absence of chest pain related to CABP	Transient, does not interfere with normal activity	Frequent, interferes with normal activity or sleep	Constant, interferes with most or all activity or sleep

The assessment of the clinical signs and symptoms of CABP will be used to determine ECR which will be calculated **programmatically**. The decision to maintain a subject on study drug therapy will be made by the Investigator, based on all available data and his or her best clinical judgment.

Subjects will be programmatically defined as a **Responder** if the following 4 criteria are met:

- Alive.

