- A by-pathogen microbiological response of persistence and a by-subject microbiological response of failure at the EOT Visit will be carried forward to the TOC Visit. If a followup specimen for culture was not obtained and the pathogen/subject was not a microbiologic persistence/failure at EOT, microbiological response at the TOC Visit will be determined based on IACR at the TOC Visit. If the IACR at the TOC Visit is indeterminate, the microbiological response at the TOC Visit will be indeterminate, unless a followup specimen for culture was obtained.
- A by-pathogen microbiological response of persistence and a by-subject microbiological response of failure at the TOC Visit will be carried forward to the LFU Visit. If a followup specimen for culture was not obtained and the pathogen/subject was not a microbiologic persistence/failure at TOC, microbiological response at the LFU Visit will be determined based on IACR at the LFU Visit. If the IACR at the LFU Visit is indeterminate, the microbiological response at the LFU Visit will be indeterminate, unless a followup specimen for culture was obtained.
- For the analysis of microbiological response at the EOT, TOC and LFU Visits in the microITT and microITT-2 Analysis Sets, where microbiological response may be missing (indeterminate), all subjects who meet the analysis set criteria will be included in the denominator.
- For the analysis of microbiological response at the EOT, TOC and LFU Visits in the ME Analysis Sets, subjects with a missing (indeterminate) microbiological response will not be included in the analysis, since by definition, subjects in the ME Analysis Sets cannot have a missing microbiological response.

For all other outcome measures, missing data are handled as follows:

- Missing values for individual data points will remain as missing. Missing values will not be imputed and only observed values will be used in data analyses and presentations.
- When individual data points are missing, categorical data will be summarized based on reduced denominators (ie, only subjects with available data will be included in the denominators).

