- j: Study personnel will evaluate signs and symptoms of CABP at Baseline, daily while on study therapy, and at EOT, TOC, and LFU Visits. **NOTE:** If Screening and Day 1 are the same day, signs and symptoms of CABP do not need to be repeated on Day 1. If EOT and the last day of study drug are the same day, signs and symptoms of CABP should be done only once on that day (i.e., as part of the EOT assessment). Signs and symptoms are not obtained at TOC or LFU if the subject was previously deemed to have an IACR of Failure.  
**OUTPATIENTS:** Study personnel will contact subjects daily by telephone to track signs and symptoms of CABP; **however, subjects must report to the study site for the assessment of CABP signs/symptoms 96 ± 24 hours after the first dose of study drug.** *See Footnote c.*

- k: Record AEs from the signing of the ICF through TOC and SAEs from signing of the ICF through LFU. Study personnel will follow unresolved AEs and SAEs present at LFU until resolution or stabilization. In addition, study personnel will monitor AEs for OUTPATIENTS in conjunction with daily telephone contacts for CABP signs/symptoms and at the study site visit 96 ± 24 hours after the first dose of study drug. *See Footnote c.*
- l: **At each required time point, ECGs should be recorded in triplicate within a 5-minute interval.** The subject should be stabilized in a supine position for 5 min before recording the ECG. If Screening and Day 1 are on the same day, the Screening ECG can serve as the Day 1 ECG prior to the first dose of study drug; an additional ECG must be performed 1-3 hours after administration of first dose. *See Footnote m.*
- m: **INPATIENTS:** The Day 4 ECG in triplicate is required prior to the first dose of study drug and again within 1-3 hours after the first dose of study drug.  
**OUTPATIENTS:** The Day 4 ECG can be performed at the required study site visit 96 ± 24 hours after the first dose. *See Footnote c.* The Day 4 ECG in triplicate is required prior to the first dose of study drug and again within 1-3 hours after the first dose of study drug.
- n: A complete physical examination is performed at Baseline and directed physical examinations are performed thereafter.
- o: **INPATIENTS:** On Day 4, a directed physical examination will be performed.  
**OUTPATIENTS:** A directed physical examination will be performed at the study site visit scheduled 96 ± 24 hours after the first dose. *See Footnote c.*

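### Full symptom resolution at TOC and LFU is calculated only in subjects with data, and earlier treatment failures and deaths have none, so the figures are conditional on not having failed or died

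*SAP*

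**What the plan says.** SAP 8.5.4.1 plans two displays of CABP signs and symptoms: a shift table against baseline at each time point, assigned to the ITT Analysis Set, and a resolution summary: "The proportion of subjects with resolution of all baseline signs and symptoms will also be provided by study visit". Both fall under one restriction: "Analyses of signs and symptoms will only be assessed in subjects with non-missing assessments of all baseline signs and symptoms at the specified visit".

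Protocol 6.11 sets the collection rule: "Signs and symptoms are not obtained at TOC or LFU if the subject previously had an IACR of Failure". Footnote j of protocol Table 1 and of SAP Appendix A repeats it; the SAP wording is "Signs and symptoms are not obtained at TOC or LFU if the subject was previously deemed to have an IACR of Failure". The visit itself still takes place. Footnote e of protocol Table 1 says: "All subjects will have a TOC Visit irrespective of early clinical failure or receipt of an alternative antibiotic".

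SAP 7.6 does not bring the missing subjects back. For outcomes other than ECR, IACR and microbiological response it says "Missing values will not be imputed and only observed values will be used in data analyses and presentations", and that "categorical data will be summarized based on reduced denominators".

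The next paragraph of SAP 8.5.4.1 summarises ECR by visit. There the denominator keeps deaths and "those subjects who have received an antibiotic for the treatment of CABP up through the relevant visit".

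**The concern.** Symptom data at TOC and LFU are missing by rule, and the trigger is treatment failure. A subject who fails at EOT attends TOC but has no symptoms recorded and so leaves the resolution denominator. The same happens at LFU after a failure at EOT or TOC. Deaths leave as well. Missingness is therefore determined by outcome, and the observed-case proportion answers a narrower question than its description suggests: among subjects who had not already failed or died, how many had full resolution?

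Three consequences follow for a reader of these tables.

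- The TOC and LFU rates look better than a rate that counts failures as not resolved.
- The series can rise from EOT to TOC to LFU partly because failures drop out.
- A shift table assigned to the ITT set does not hold the ITT set at those visits.

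The SAP text makes this easy to miss. Its parenthesis on when symptoms are collected lists TOC and LFU without mentioning the failure exception.

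**Working it through.** The plan states no figure for symptom resolution, so there is none to reproduce. The check has two parts.

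**1. Who is absent, by rule**

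| Visit | Absent from the resolution and shift displays | Kept in the ECR-by-visit denominator |
|---|---|---|
| TOC | IACR failure at EOT; death before TOC | Deaths; recipients of a CABP antibiotic |
| LFU | IACR failure at EOT or TOC; death before LFU | Deaths; recipients of a CABP antibiotic |

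The collection rule applies to a previous failure. A subject first judged a failure at TOC can still have TOC symptoms and is lost only at LFU. The share lost at TOC is therefore no larger than at LFU.

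In protocol 6.12.1 every criterion for IACR failure other than death involves non-study antibacterial therapy. The ECR-by-visit denominator thus retains essentially the subjects whom the resolution display drops.

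**2. Size**

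Let r be the resolution rate among subjects with data and f the share with an earlier failure or death. Other missing data are set aside.

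- Rate under the SAP rule: r
- Rate with earlier failures and deaths counted as not resolved: r × (1 − f)
- Excess: r − r(1 − f) = r × f

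The documents give neither r nor f, so both are assumed. The top of the range for f is taken from the 80% mITT success rate in SAP 7.1: failure plus indeterminate at TOC would be 20%, or 0.20 × 369 ≈ 74 subjects per arm. That is a ceiling for failures at TOC at the planning rate, not an estimate of them.

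Excess in percentage points:

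| r | f = 5% | f = 10% | f = 15% | f = 20% |
|---|---|---|---|---|
| 50% | 2.5 | 5.0 | 7.5 | 10.0 |
| 70% | 3.5 | 7.0 | 10.5 | 14.0 |
| 90% | 4.5 | 9.0 | 13.5 | 18.0 |

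**Between arms, with r equal in both** (the SAP rule then shows a difference of 0):

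- r = 60%, f = 15% v 10%: 0.60 × 0.85 = 51% v 0.60 × 0.90 = 54%, difference −3 points
- r = 70%, f = 20% v 10%: 56% v 63%, difference −7 points
- r = 90%, f = 20% v 10%: 72% v 81%, difference −9 points

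**With r unequal**, the larger excess need not fall in the arm with more failures. An arm with r = 50% and f = 15% has an excess of 7.5 points; an arm with r = 90% and f = 10% has 9.0.

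**The case against.** The strongest reply is that nothing important depends on this display. SAP 8.5.4 makes it an additional, descriptive analysis with no non-inferiority conclusion; no confidence interval is specified for it, and it is not among the listed outcomes in SAP 6.2 and 6.3. The restriction is stated openly and matches the general rule in SAP 7.6. This stands, and it limits the weight of the point.

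A reader might infer that a real disadvantage of one arm is hidden. The documents do not support that. IACR at TOC in the mITT set carries EOT failures forward and reports failures by arm with a confidence interval (SAP 7.6 and 8.5.3.1). IACR at LFU has its own prior-failure category (SAP 6.2.1 and 8.5.4.1). Mortality to Day 28 is reported in the ITT set (SAP 8.5.3.5). The imbalance is missing from this table, not from the trial report.

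It can also be said that alive status and absence of a CABP antibiotic are components of the ECR definition (SAP 6.1), whereas resolution describes symptom state alone. Different denominators for different measures are then not a contradiction. That is fair: the ECR-by-visit paragraph is a precedent, not proof of an error. Some failed subjects may also have resolved on rescue treatment by LFU. But their symptoms are not collected, so the observed data cannot answer that question, and the display still needs to say whom it covers.

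Finally, the sizes are illustrative. A difference of −3 points is less than one standard error with 369 per arm: √[(0.51 × 0.49 + 0.54 × 0.46)/369] ≈ 3.7 points.

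**Conclusion.** The point holds for the TOC and LFU columns of the resolution summary and the symptom shift table. As planned, they are conditional on not having failed or died earlier, and no other section restores those subjects. If earlier failures and deaths count as not resolved, the reported rate is too high by r × f, which is 2.5 to 18 points over the assumed ranges. This rests on that composite definition and on assumed values of r and f.

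Three stronger readings are not supported.

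- The overstatement is not necessarily greater in the arm with more failures; that follows only if resolution among subjects with data is equal in the two arms.
- The ITT label belongs to the shift table; the sentence on the resolution proportion names no analysis set.
- Primary ECR and IACR at TOC are not affected.

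The consequence is confined to how these descriptive tables are read. The change is still worth making, because SAP 8.5.4 presents these analyses as support for the main efficacy findings.

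**What to change.** In SAP 8.5.4.1, for TOC and LFU:

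- Keep in the resolution denominator, as not resolved, subjects who died, received a non-study antibacterial for CABP, or had an IACR of Failure before that visit's assessment. The ECR-by-visit denominator already retains deaths and CABP antibiotic recipients.
- Add a prior failure/death category to the TOC and LFU shift tables.
- Keep the observed-case version as a supplement, with the number of excluded failures and deaths shown by arm beside each rate.

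The cost is a short SAP amendment and a few lines of programming. IACR, antibiotic and death data are already collected. The downside is that reported resolution rates will be lower and the measure becomes a composite instead of a pure description of symptoms, which is why the observed-case version should stay. Settling the denominator before unblinding avoids a post-hoc choice.
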